13.1.1.1. Comparability of Historical Controls

Utilization of both historical control/observational databases (UK-PBC and Global PBC Study Group), with more than 6000 subjects each, allow for a rigorous subject level meta-analysis. The historical databases include long-term follow up, detailed subject-level information such as baseline clinical characteristics, longitudinal liver biochemistry, and long-term outcomes, and span a broad range of subject characteristics that may influence disease (disease state, age, gender, and regional differences in standard of care). Historical controls from both databases will be chosen based on the same study inclusion/exclusion criteria. Propensity score matching method will be utilized to select historical controls that match the treated subjects using available covariates. The adequacy of matching will be assessed by statistical methods described under [Section 13.1.8](#).

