13.1.8. Supportive Analysis

Per the International Conference on Harmonisation (ICH) E10 guidance, “where no obvious single optimal external control exists, it may be advisable to study multiple external controls”. In order to address the risks associated with the inclusion of a long-term placebo arm, supportive analyses of the primary endpoint will compare clinical outcomes in the OCA treatment arm to historical controls, which serves as an external control for supportive analysis.

In an attempt to avoid the inherent biases with historical controls and to maintain the integrity of this comparison, one can invoke matching methods to optimize comparability and find a historical control that is “similar” to a participating subject. The historical database control should be as similar as possible to the study population and should have been exposed to a similar standard of care (see [Section 5.5.2.3](#)).

A propensity score can be used to reduce bias through matching, stratification, regression adjustment, or some combination. Propensity scores use information from a pool of patients who do not participate in the study (historical controls) to identify what would have happened to participating subjects in the absence of the treatment. By comparing how outcomes differ for treated subjects relative to historical controls, it is possible to estimate the effects of the treatment between the treated subjects and the matched natural history subjects.

A full range of covariates across which the treatment and historical controls might differ will be considered to mitigate potential bias. Although the results of using matching controls are conditional only on the observed covariates, if one has the ability to measure many of the covariates that are believed to be related to the treatment assignment, then one can be fairly confident that approximately unbiased estimates for the treatment effect can be obtained. Both UK-PBC Group and the Global PBC Study Group formally collect numerous covariates that could be used for propensity score estimation including standard of care, eg, UDCA.

Historical controls will be chosen based on the same inclusion/exclusion criteria where possible. Propensity scores will be estimated using the available covariates that predict receiving the treatment. Only covariates and not outcome variables will be included in the propensity score estimation, to avoid biased results that are in favor of one treatment.

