The covariates and factors collected in the historical databases will be specified in the SAP.

Propensity scores will be estimated first through a logistic regression model with treatment group as the dependent variable and the above covariates/factors as independent variables. Then the stratum boundaries are determined based on the propensity score values for both groups (OCA population and control [historical and randomized placebo]) combined or in the OCA population or historical control group alone. Based on recommendations in the literature, quintiles of the estimated propensity score from the combined group will be used to determine the stratum boundary cut-offs for the different strata.

The baseline characteristics between treated and natural history subjects in the matched dataset will be summarized and presented in a tabular format. Statistical methods such as Wilcoxon Rank-Sum test will be used to assess the balance for baseline covariates. The standardized difference and variance ratios for these covariates will also be calculated. In addition, box plots of propensity scores for treated and natural history subjects will be separately presented, to further assess the adequacy of matching.

A third-party statistician(s) will perform the propensity score modeling and matching. This third-party statistician(s) will be separate and independent from the statistician(s) who will assess the success of matching and perform efficacy analyses. Outcome events collected in the historical database are: death (liver-related and all-cause), liver transplant, HCC, and other. Other is defined as cirrhosis or decompensation such as ascites, variceal bleed, and encephalopathy.

The propensity score quintile will be then be used as the stratification factor in the stratified log rank test to compare randomized OCA-treated subjects in the ITT population and historical controls (Overall Historical Control Population: both the UK-PBC Group and Global PBC Study Group databases) on the following outcomes:

- Time to death (all-cause)
- Time to liver-related death
- Time to liver transplant
- Time to liver transplant or death (all-cause)
- Time to liver transplant or liver-related death

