KM estimates of the distribution of the time-to-event will be tabulated and graphed by treatment group. The tabulation will include the KM estimate of the medians and corresponding 95% CIs if the medians can be estimated. The number and percent of subjects censored and with events will be presented. The hazard ratio and 95% CI will be determined based on a Cox regression model stratified by randomization strata to estimate the magnitude of the effect.

Sensitivity analyses will be conducted limiting to the separate individual historical control databases, ie, UK-PBC Group and Global PBC Study Group. To evaluate the robustness of the propensity score estimations, additional algorithms and factors may be considered.

Although the study is designed as a placebo-controlled study, the DMC may recommend changes to study conduct based on the pre-specified interim analyses (see [Section 13.1.12](#)), including the potential use of a revised primary efficacy analysis. This analysis would compare all subjects in the OCA population, to all control subjects (randomized placebo and historical controls) on time to liver transplant or death (all-cause), using similar statistical methodology as specified above.

Notably, the planned primary analysis would not be revised without prior agreement with regulatory authorities.

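### Section 13.1.8 lets the efficacy statisticians judge the historical-control match without requiring that it be accepted and locked before they have outcomes, and offers a significance test as its example balance check

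*Protocol*

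**What the plan says.** Section 13.1.1.1 selects historical controls by propensity matching and refers the adequacy check to Section 13.1.8: "The adequacy of matching will be assessed by statistical methods described under" that section.

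Section 13.1.8 then divides the work. "A third-party statistician(s) will perform the propensity score modeling and matching", and this party is "separate and independent from the statistician(s) who will assess the success of matching and perform efficacy analyses". One group is thus named for two tasks: judging the match and analysing efficacy.

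For the balance check, the section says "Statistical methods such as Wilcoxon Rank-Sum test will be used to assess the balance for baseline covariates". It goes on: "The standardized difference and variance ratios for these covariates will also be calculated". It also asks for "box plots of propensity scores for treated and natural history subjects will be separately presented, to further assess the adequacy of matching". It gives no limit for any of these measures and does not say which one decides.

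Outcomes are kept out of the score itself: "Only covariates and not outcome variables will be included in the propensity score estimation, to avoid biased results that are in favor of one treatment". Section 13 requires the SAP to be approved before the first interim analysis, before propensity scoring and before unblinding. Section 5.5.2.3 calls the historical comparison supportive and separate from the placebo comparison. The end of Section 13.1.8 allows for a possible revised primary analysis that pools historical controls with placebo, subject to prior agreement with regulators.

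**The concern.** A propensity-matched comparison is credible when the design stage, including the decision that the match is good enough, is finished before anyone making that decision can see how the outcomes fall. Section 13.1.8 separates the matcher from the outcome analyst. It then gives the accept-or-reject decision to the outcome analyst.

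Trial blinding does not protect this step. Balance is tabulated for treated against natural-history subjects, so the assessor must know who received OCA. The historical outcomes are already in the databases, as Section 13.1.8 itself lists.

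The decision also has consequences. Section 13.1.1 defines all three historical control populations by demonstrated comparability, so whoever judges the match settles who is in the comparator. Section 6.2 makes the comparison with historical controls a secondary objective.

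The choice of example adds to the problem. A p-value for balance mixes the size of an imbalance with the number of subjects, so a non-significant result does not show that the groups are close.

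**Working it through.** **1. Who holds which step (Protocol)**

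| Step | Assigned to | Kept from outcomes? |
|---|---|---|
| Analysis method | SAP, approved before scoring and unblinding (Section 13) | Yes, by timing |
| Propensity model | Third party (13.1.8) | Yes, outcomes excluded from the model |
| Matching | Third party (13.1.8) | Third party is independent of the efficacy statisticians |
| Accepting the match | Efficacy statisticians (13.1.8) | Not stated |
| Efficacy analysis | Same statisticians (13.1.8) | Not applicable |

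The fourth row is the gap. Approving the SAP early fixes the method, but the match is judged later, on real data. Leaving outcomes out of the model protects estimation of the score, not its acceptance.

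**2. The plan's own figures**

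The protocol gives no figure for match adequacy. The arm size comes from Section 13.1.2: 428 subjects at 1:1, so 428 / 2 = 214 on OCA. The 428 reproduces closely. Under the stated survival, accrual and follow-up assumptions the average event probability is 0.3308, so 127 / 0.3308 = 384, and 384 / 0.9 = 427.

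**3. What a Wilcoxon test lets through**

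Assumptions: a normally distributed covariate shifted between groups, Wilcoxon relative efficiency 3/π = 0.955, and two-sided 0.05. The protocol does not state the number of matched controls m, so a range is shown.

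SE = √[(1/214 + 1/m) / 0.955], and the largest non-significant observed standardized difference is 1.96 × SE.

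For m = 214: SE = √[(2/214) / 0.955] = 0.0989, and 1.96 × 0.0989 = 0.194.

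| Controls m | Largest non-significant difference |
|---|---|
| 214 (1:1) | 0.194 |
| 428 (1:2) | 0.168 |
| 856 (1:4) | 0.153 |
| 1070 (1:5) | 0.150 |
| 6000 | 0.140 |

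Even with 6000 controls the figure stays at 0.14, because the 214 OCA subjects limit the precision.

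The chance of a non-significant result for a true difference d is 1 − Φ(d/SE − 1.96) − Φ(−d/SE − 1.96):

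| True d | 1:1 | 1:4 |
|---|---|---|
| 0.1 | 83% | 75% |
| 0.2 | 48% | 28% |
| 0.3 | 14% | 3% |
| 0.5 | 0.1% | <0.1% |

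Simulation with 3,000 runs per cell agrees: 83%, 47%, 14% and 0.1% at 1:1, and 75%, 29%, 3% and 0% at 1:4. Used alone, the test would often pass small to moderate imbalance and would almost never pass a large one.

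**4. What such an imbalance could do**

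If one covariate carries a hazard ratio of g per SD and differs by 0.19, the unadjusted treatment hazard ratio is multiplied by exp(−0.19 × ln g) when the controls are the sicker group. This gives 0.93 for g = 1.5, 0.88 for g = 2.0 and 0.84 for g = 2.5. The values of g are assumed. The calculation also ignores the stratification of the log-rank test by propensity quintile, which would adjust for part of the difference. It illustrates the scale and is not an estimate.

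**The case against.** The strongest reply is that the plan already has most of the right parts. The matcher is independent, outcomes are excluded from the score, and the SAP precedes scoring and unblinding. Standardized differences, variance ratios and box plots are all required, and Wilcoxon appears only as an example. Numerical limits are commonly left to the SAP, which is not at hand. The comparison is supportive, and a revised primary analysis needs regulators' prior agreement. Separating the matcher from the assessor is also a merit, because matchers do not then grade their own work.

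All of this is correct, and it rules out three stronger readings that a reader might infer.

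- *The match will be chosen after outcomes are seen.* The protocol does not say so. It is silent on the order of events, which leaves the possibility open but does not plan for it. The size of any selection effect cannot be derived, since no section gives the number of candidate matches or how far their results would agree.
- *A Wilcoxon test decides and passes large imbalance.* It is not the only check, and a difference of 0.5 would pass about 0.1% of the time at 1:1.
- *The efficacy team may replace the match with another algorithm.* The sentence "To evaluate the robustness of the propensity score estimations, additional algorithms and factors may be considered" names no actor and stands in a paragraph on sensitivity analyses.

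None of these points removes the role assignment. It is stated in the protocol, so it is not a detail left to the SAP, and none of the safeguards listed covers acceptance of the match.

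**Conclusion.** The point holds and is worth correcting. Section 13.1.8 gives acceptance of the match to the statisticians who analyse outcomes, and the protocol does not require acceptance and locking before they have outcome data. The supportive comparison is therefore not protected from outcome-aware acceptance. The same weakness would carry into the possible pooled primary analysis, which is to use similar methodology.

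The balance issue is secondary. A Wilcoxon p-value is a poor deciding measure because an observed difference of up to about 0.19 is non-significant at 214 against 214, or about 0.15 at 1:4 to 1:5. These figures rest on a normal shift model and an assumed matching ratio. The better measures are already planned but are not made decisive.

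The randomized comparison of OCA with placebo is not affected. The SAP may already set limits or a lock. If so, Section 13.1.8 needs only to be brought into line with it.

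**What to change.** In Section 13.1.8, state that:

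- match adequacy is assessed by statisticians without access to outcomes, who may remain independent of the matcher;
- the standardized differences and variance ratios already planned are the deciding measures, against limits set in advance (for example, an absolute standardized difference below 0.10 for every covariate), and Wilcoxon p-values are descriptive only;
- the accepted matched set is locked and dated before outcomes are linked.

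The SAP should carry the limits. The cost is a few sentences and an assessor without outcome access, with no change to the conduct of the trial. The downside is that a match that fails must be redone while still blind to outcomes, or reported as inadequate.

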5.5.2.3. Rationale for Control Groups

Placebo Control Group

The use of a randomized placebo control group added to established standard of care provides the best scientific evidence of efficacy and safety. The use of a placebo control provides a concurrent comparator group, accounting for not only a placebo effect but a standard of care effect. Notably, accounting for the standard of care effect is critical when designing an outcome-based study conducted globally when there are regional differences in the treatment of subjects with PBC.

Historical Control Group

The available robust historical PBC observational datasets (UK-PBC and Global PBC Study Group) will also be leveraged to provide further comparative evaluation of the clinical benefit of OCA. Each database includes >6000 patients with long-term follow-up.

Comparison of OCA treatment to the historical controls may provide utility in addressing potential bias or confounds associated with the placebo arm. For example, bias associated with the potential addition of commercial OCA and/or differences in long-term standard of care between the treatment arms including ancillary treatments and diagnostics.

Therefore, further evaluation of the effect of OCA will compare OCA treatment versus historical controls, and will be supportive to placebo comparisons (ie, comparisons to historical and placebo controls will be evaluated separately).

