9.4. Randomization and Blinding

This study will be conducted in a double-blind, placebo-controlled manner. Allocation to one of two treatment groups (OCA or placebo) will occur on a 1:1 ratio across sites and will be stratified by UDCA treatment (yes/no) and mean baseline bilirubin categories ($>ULN/\leq ULN$), as specified by the central laboratory. The randomization will be based on a predefined randomization code (generated by the Sponsor or designee) using an interactive web response system (IWRS), which the Sponsor intends will serve as a computer-based subject registration system at Screening and Day 0. The IWRS will also serve as an investigational product inventory and management system and may be integrated with the study database.

The Investigator or designee will be required to register the subject in the IWRS and may be prompted to provide subject data necessary to properly randomize and allocate the subject to treatment. A randomization number will be assigned (refer to [Section 9.5.2](#) below) and investigational product dispensing information (ie, bottle number[s]) will be provided.

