13.1. Efficacy Analysis

13.1.1. Analysis Populations

The following subject populations will be evaluated and used for presentation and analysis of the data:

- The Intent-to-Treat (ITT) Population will include all randomized subjects who receive any amount of investigational product (OCA or placebo). The ITT Population will be the primary population used for efficacy analyses. Treatment assignment will be based on the randomized treatment.
- The Per Protocol (PP) Population will include all ITT subjects who do not have any major protocol violations that potentially affect the efficacy conclusion. Treatment assignment will be based on the randomized treatment.
- The Safety Population will include all subjects who received any amount of investigational product (placebo or OCA). The Safety Population will be the primary population used for safety analyses. Treatment assignment will be based on the treatment actually received.
- The PK Population will include all OCA subjects who have at least one confirmed fasted analyzable sample. Subjects must have been fasting for approximately 8 hours prior to the visit and must not have any major protocol deviations that potentially affect exposure levels. The PK population will be used for OCA PK analyses.
- The Overall Historical Control Population will include subjects from the United Kingdom (UK) -PBC Group and Global PBC Study Group databases with demonstrated comparability to randomized subjects in this clinical study (747-302) with respect to both subject characteristics and disease progression.
- The UK-PBC Historical Control Population will include subjects from the UK-PBC Group databases with demonstrated comparability to randomized subjects in this clinical study (747-302) with respect to both subject characteristics and disease progression.

- The Global PBC Historical Control Population will include subjects from the Global PBC Study Group database with demonstrated comparability to randomized subjects in this clinical study (747-302) with respect to both subject characteristics and disease progression.

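### Section 13.1.8 tests OCA against historical controls within propensity quintiles but takes the hazard ratio from a Cox model stratified by randomization strata

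*Protocol*

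**What the plan says.** Protocol section 13.1.8 compares OCA-treated ITT subjects with historical controls on five time-to-event outcomes. For the test: "The propensity score quintile will be then be used as the stratification factor in the stratified log rank test". For the estimate of the same comparison: "The hazard ratio and 95% CI will be determined based on a Cox regression model stratified by randomization strata".

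Section 9.4 shows what the randomization strata are; allocation is "stratified by UDCA treatment (yes/no) and mean baseline bilirubin categories" (above ULN or not).

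Three other statements bear on how controls are chosen:
- Section 13.1.1 defines all three historical populations as subjects "with demonstrated comparability to randomized subjects in this clinical study (747-302) with respect to both subject characteristics and disease progression".
- Section 13.1.1.1 gives the selection method: "Propensity score matching method will be utilized to select historical controls that match the treated subjects using available covariates".
- Section 13.1.8 restricts the score: "Only covariates and not outcome variables will be included in the propensity score estimation".

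Section 13.1.8 closes with a contingency. On the basis of the interim analyses the DMC may recommend changes, "including the potential use of a revised primary efficacy analysis". That analysis would set OCA against randomized placebo pooled with historical controls, on transplant or death, by methods similar to those given earlier in the section. Prior regulatory agreement is required.

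**The concern.** A log-rank test and a Cox model stratified by the same factor belong together: the stratified log-rank test is the score test of the stratified Cox model. With different strata, the p-value and the confidence interval adjust for different things and can disagree on whether there is an effect.

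Here the weaker adjustment sits on the estimate. Section 13.1.8 promises a full range of covariates to limit bias from non-randomized controls and summarises them in the propensity score. The hazard ratio then uses two binary factors. The sentence matches the one in section 13.1.3 for the randomized comparison, where it is appropriate, and appears to have been carried over. Any imbalance left after matching would therefore be reduced by the quintiles in the test but left largely in place in the reported hazard ratio.

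The population wording in section 13.1.1 raises a related, smaller issue. Read literally, comparability in disease progression admits controls on their post-baseline course, which is what the comparison sets out to measure.

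**Working it through.** **1. What each model adjusts for.** Randomization strata: UDCA (2 levels) × bilirubin (2 levels) = 4 cells. Propensity strata: 5 quintiles of a score built from the available covariates. Section 13.1.1.1 says the databases hold longitudinal liver biochemistry, and section 13.1.8 says they record UDCA, so the 4 cells can be derived for historical controls. Within a cell, imbalance in any other prognostic covariate is untouched.

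**2. Plan's own figure.** Section 13.1.8 gives no effect size, number of controls or matching ratio for this comparison, so there is nothing to reproduce. The OCA arm size follows from section 13.1.2: 428 / 2 = 214.

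**3. Size, by simulation.** From the protocol: 214 OCA subjects, and follow-up between 6 and 10 years (4 years of accrual plus 6 of follow-up). Assumed, because the documents do not give them: a true hazard ratio of 1, the number of controls, the covariate effects, and how much sicker the controls are.

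- Set-up A: 1000 unmatched controls; one prognostic score with log hazard ratio 0.7 per SD; baseline hazard 0.03 per year; 85% on UDCA; bilirubin category partly driven by the score; 100 replicates.
- Set-up B: 2000 unmatched controls; four covariates with log hazard ratio 0.5 per SD each; 40 replicates.
- Set-up C: as B, after 1:1 nearest-neighbour matching; 40 replicates.

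| Set-up | Controls sicker by | HR, randomization strata | HR, propensity quintile | Ratio |
|---|---|---|---|---|
| A | 0.25 SD | 0.87 | 0.96 | 0.87/0.96 = 0.91 |
| A | 0.5 SD | 0.79 | 0.99 | 0.79/0.99 = 0.80 |
| B | 0.125 SD on each | 0.82 | 0.96 | 0.82/0.96 = 0.85 |
| B | 0.25 SD on each | 0.68 | 0.94 | 0.68/0.94 = 0.72 |
| C | 0.125 SD on each | 0.94 | 0.93 | 0.94/0.93 = 1.01 |
| C | 0.25 SD on each | 1.04 | 1.04 | 1.04/1.04 = 1.00 |

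In set-up A the share of replicates significant at a nominal 5% was 16% (randomization strata) against 9% (quintile) at 0.25 SD, and 34% against 5% at 0.5 SD.

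Replicate numbers are small. Other runs at the nominal settings of B gave 0.85 at 0.125 SD, and 0.69 and 0.75 at 0.25 SD, for the randomization-strata model. Another run of C gave about 0.97 to 1.00 for all models. Only the pattern is firm: a clear gap without matching, none that can be seen after close matching.

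**4. Disease progression.** Section 13.1.1 admits controls comparable in progression. Section 13.1.1.1 selects on covariates, and section 13.1.8 keeps outcomes out of the score. The three agree only if progression means stage at baseline, which section 13.1.1 does not say.

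**The case against.** The best defence is that the controls are to be matched first. Section 13.1.1.1 selects them by propensity matching, section 13.1.8 checks balance in the matched dataset, and a third-party statistician does the modelling and matching. On matched controls the Cox model as written is a second, partial adjustment, not an unadjusted estimate, and its strata can be derived. This stands. A reader might infer from the unmatched figures that the plan's hazard ratio would be biased to around 0.7 or 0.8. The documents do not support that, because they do not plan an unmatched comparison. What remains is the mismatch itself, and exposure to whatever imbalance the matching leaves.

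On progression, the operating rules in sections 13.1.1.1 and 13.1.8 use covariates only, and no passage gives a procedure for selecting on outcome. That also stands, and it reduces the matter to an ambiguous phrase.

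A reader might also infer that the DMC can make this historical comparison the primary analysis, or that the trial's type I error is already inflated. Neither follows. The DMC may only recommend; sections 13.1.8 and 13.1.12 require prior agreement with regulators; and the contingent analysis pools placebo with historical controls, so it is a different comparison. Working out a best-of-two error rate, 0.042 to 0.045 one-sided instead of 0.025, assumes a free choice between two final results, which the text does not grant.

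**Conclusion.** The mismatch is real and lies within section 13.1.8 itself, so it does not turn on what the SAP may add. The hazard ratio and confidence interval against historical controls omit the propensity-quintile adjustment that the accompanying test has.

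The bias depends on match quality: near zero after close matching, material only if matching is loose or imperfect. The unmatched ranges (0.68 to 0.87 against 0.94 to 0.99, true value 1) illustrate the exposure under assumed covariate effects and shifts; they do not forecast the result. The direction assumes controls sicker than trial subjects, and healthier controls would push the estimate the other way.

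Severity is moderate. Sections 5.5.2.3 and 13.1.8 make the comparison supportive, and the randomized primary analysis in section 13.1.3 is not touched. The error gains some weight because the contingent revised primary would borrow the methods of section 13.1.8, possibly including this Cox model.

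One matter to note, without asking for a change: that contingency sits in tension with section 5.5.2.3, where "comparisons to historical and placebo controls will be evaluated separately", and the protocol states no type I error control for it. Whether to keep it is a debatable design choice.

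**What to change.** - Section 13.1.8: state that the Cox model is stratified by propensity score quintile, as the log-rank test already is. If matched sets are preferred, stratify both test and model by matched set. The same strata should govern both.
- Section 13.1.1: in all three historical population definitions, replace disease progression with baseline disease stage, so that selection rests on baseline information, consistent with sections 13.1.1.1 and 13.1.8.

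Both are wording changes to the protocol, to be carried into the SAP where it repeats the text. They need no new data, no added subjects and no change to the randomized analysis.
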